6. PATIENT SELECTION AND PLANNED NUMBER OF PATIENTS

Patients are eligible for inclusion in this NIS if they have taken anastrozole either upfront or following two to three years of tamoxifen treatment (“switch”) for at least three and not more than six months prior to offering an individual participation in this program. Treatment should follow local therapy guidelines and standard practice. Treatment decisions for patients participating in this study including assessments or supportive therapy during follow-up visits will also follow guidelines and remain independent of the program.

The patient population will include postmenopausal women with hormone-receptor positive primary breast cancer scheduled for adjuvant upfront endocrine treatment with anastrozole or following two to three years of tamoxifen treatment (“switch”) according to the current SmPC (Appendix C). Patients will have taken anastrozole for at least three months and not more than six months before the start of the study.

It is planned to enrol and document 3212 patients in this NIS. Further details regarding the objectives and the sample size consideration can be found in Section 3 and 11.5..

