8.1.1 Documentation at registration

The following data should be documented at registration/enrolment

Demographics	Year of birth
Patient number	
Patient insured in a sick fund part of GWQ?	Yes; no
Informed consent	
Inclusion / exclusion criteria	
Was the patient identified for anastrozole therapy 1mg / day?	Yes; no
Date of the 1 st prescription	
Start date of anastrozole therapy	
Breast centre that performed surgery	Name Address
Investigator details	Fax number E-mail address Name

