Arthralgia questionnaire	
Arthralgia onset during anastrozole therapy (no, yes, unknown – if yes : localisation, swelling, pain intensity; duration, relationship to study drug) Therapy of arthralgias: no, yes – please specify.
 
Assessment of treatment with medication (drug name, dose, package size, duration (start-end))
 
Doctor`s visits (including doctor`s specification)
 
Diagnostics? if yes => specify
 
Physiotherapy? if yes => specify
 
Adjuvants? if yes => specify
 
Lifestyle changes? if yes => specify

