8.1.3 Documentation after 3, 6, and 9 months after study start

The following patient data should be documented after 3, 6, and 9 months after study start or at the time point of treatment discontinuation:

Observation interval	Date of last examination Date of documentation (current date)
Date of observation	
Patient lost to follow-up status	If the patient does not attend follow-up visits, can she be contacted (yes, no – lost to follow-up)
Demographics	Weight (kg)
Occurrence of adverse events	(no, yes) ⇒ AE/SAE-module
Status of breast cancer disease	Loco-regional recurrence / contralateral recurrence / distant metastasis (if yes: date of recurrence / localisation?)
Survival status	(alive, died) ⇒ Survival –module
Continuation of anastrozole therapy (yes, no)	Yes ⇒ Treatment continuation-module No ⇒ Treatment discontinuation module Change of endocrine therapy ⇒ Switch module
Patient continuation of participation in COMPACT	(Yes, no – consent withdrawn, no – died, no – other reasons) ⇒ Consent withdrawal-module
Concomitant medication	No, yes => please specify

The following data should be documented after 3, 6, and 9 months of endocrine therapy or at the time point of treatment discontinuation as indicated and applicable by patient's status:

Treatment continuation – Module (continuation of anastrozole therapy)	
Treatment compliance: doctor's assessment	Estimation of compliance by doctor's judgement: "How many tables have been taken in the observed period?" (none, few, less than half, appr. half, more than half, almost all, all)
Number of medicines / tablets or capsules per day	
Anastrozole prescriptions / sample packages	Number and package size
Was anastrozole intake stopped / taken irregularly?	if yes => reason?
Concomitant medication	No, yes => please specify

Arthralgia – Module (to be filled in in case of arthralgia occurrence during anastrozole therapy)	
Arthralgia questionnaire	
Arthralgia onset during anastrozole therapy (no, yes, unknown – if yes : localisation, swelling, pain intensity; duration, relationship to study drug)
 
Therapy of arthralgias: no, yes – please specify.
 
Assessment of treatment with medication (drug name, dose, package size, duration (start-end))
 
Doctor's visits (including doctor's specification)
 
Diagnostics? if yes => specify
 
Physiotherapy? if yes => specify
 
Adjuvants? if yes => specify
 
Lifestyle changes? if yes => specify

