	
- don't like it
 
Why don't you like taking your medication?
 
 - difficulties in swallowing tablets - disturbs my daily routine - reminds me of my disease - other 
Compliance to anastrozole: You were supposed to take one tablet anastrozole per day. However, daily medication intake may be forgotten. How many anastrozole tablets did you actually take from the start of anastrozole therapy until today:
 
 - none - few - less than half - almost the half - more than half - almost all - all

Breast cancer and therapy
	
Do you have the feeling that you have a voice in concern of your breast cancer medication? (no, few, satisfactory, good)
 
Were the effects of the anti-hormone therapy and the scheduled drug explained to you? (no, few, satisfactory, good)
 
Were the side effects of the anti-hormone therapy and the scheduled drug explained to you? (no, few, satisfactory, good)
 
Did you receive any sample of anastrozol? (no, yes, if yes, how many?, I don't know)

Questions on arthralgia occurrence, characteristics and management
	
Did you experience any arthralgias? (yes, no)
 
Did you experience any arthralgias before the start of anastrozole treatment? (no, yes => which medication did you take?)
 
Did you experience any arthralgias since you started anastrozole treatment? (no, yes)
 
Which medication did you take because of arthralgias?
 
Did you consult any doctor because of arthralgias, and in which field did the doctor specify? (general practitioner,

	
number of times; internist, number of times; orthopedist, number of times; rheumatologist, number of times; pain therapist, number of times; gynaecologist, number of times)
 
Which diagnostic measures did you undergo during your doctor`s visit? (X-ray, CT, MRT, Ultrasound)
 
Were you admitted to hospital due to arthralgias?
 
Did you receive any physiotherapy? (yes, no, if yes => therapy method; number of prescribed therapies)
 
Performance of any regular sportive action? If yes, how often?
 
VAS scale: Rheumatoid Arthritis Symptom Questionnaire (see appendix E)

Questions about medication side effects	GASE-P: Generic Assessment of Side Effects (appendix E)
Somatosensory amplification of side-effects	SASS, Somatosensory Amplification Scale (appendix E)
Patient`s belief about medicines	BMQ, Beliefs about medicines questionnaire (appendix E)

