8.2.2 Documentation at 3, 6 an 9 months after study start

The following data should be documented after 3, 6 and 9 months after study start or at the time point of treatment discontinuation

Demographics	Year of birth
Observation interval	Date of assessment
Demographics	Year of birth

Observation interval	Date of assessment
Medication intake	
Daily intake of drugs/tablets apart from the prescribed anti-cancer agent?
 
Number of drugs and tablets per day? (none, unknown)
 
Self reported medication intake (questions from reference): Do you occasionally forget taking of your medicine ? (yes,

	
no)
 
Are you occasionally neglectful concerning your medicine intake? (yes, no)
 
When you feel better, do you occasionally stop taking your medicine? (yes, no)
 
Sometimes when you feel worse, do you stop taking your medicine? (yes, no)
 
How do you feel about taking your medication?
 
 - never mind - don't like it 
Why don't you like taking your medication?
 
 - difficulties in swallowing tablets - disturbs my daily routine - reminds me of my disease - other 
Compliance to anastrozole: You were supposed to take one tablet anastrozole per day. However, daily medication intake may be forgotten. How many anastrozole tablets did you actually take from the start of anastrozole therapy until today:
 
 - none - few - less than half - almost the half - more than half - almost all - all

Questions on arthralgia occurrence, characteristics and management
	
Did you experience any arthralgias during the past three months? (yes, no)
 
Did the arthralgia intensity change during the past three months? (yes, the intensity decreased; yes, the intensity increased; no)
 
Which medication did you take because of arthralgias?
 
Did you consult any doctor because of arthralgias, and in which field did the doctor specify? (general practitioner, number of times; internist, number of times; orthopedist, number of times; rheumatologist, number of times; pain

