Subjective perception of side-effects will be evaluated using the following scores: GASE-P (Generic Assessment of Side Effects, appendices E and F), SASS (Somatosensory Amplification Scale, appendices E and F), and BMQ (Beliefs about medicines questionnaire, appendices E and F).

Arthralgia therapy and related costs

Arthralgia therapy will be documented in the eCRF and in the patient questionnaire (for further information, see Chapter 8; e.g., newly prescribed medication, doctor’s visits, diagnostics, hospital admissions). Diagnostic and therapeutic measures will be recorded as standardised patterns in the eCRF and in the patient questionnaire and will be correlated with itemised costs for evaluation purposes. Cost evaluations will be feasible on patient and global level.

Each occurrence of arthralgia will be assigned to the corresponding time interval according to 0-3, 3-6, 6-9, 9-12 and 12+ months after the start of anastrozole treatment (i.e. post treatment start).

Validation of data (arthralgia therapy and compliance) by sick fund data

For patients who signed an additional informed consent form (Appendix C, see chapter 7.3), arthralgia therapy as documented by the investigators and the patients will be compared to sick fund data on an individual patient level by a third party who will combine the study and the sick fund datasets on an individual patient level. The third party will combine the sick fund dataset and the study dataset using the patient insurance number which will be sent to on the additional informed consent (Appendix C). The patient insurance number will be immediately deleted after data combination. Statistical evaluation will only be based on pseudonymised data.

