11.4.1 Outcome variables

The objectives outlined in chapter 3 will be analysed as follows:

Primary objective:

Assessment of arthralgia scores and patients' compliance within the first year of anastrozole treatment¹, stratified by upfront and switch therapy as well as assessment of the relationship between compliance and arthralgia scores.

The absolute number and percentage of compliant patients will be calculated. Groups will be compared with Fisher's exact test

From the arthralgia scores an overall score will be calculated (sum of 14 single item scores divided by 14). Groups will be compared using t-test.

Relationship between compliance and arthralgia scores will be assessed using logistic regression analysis.

Of primary interest are the 3 months data (data obtained within the first three months of anastrozole therapy). Secondly, the other time points will be evaluated.

Secondary objectives:

Incidence of arthralgias and arthralgia characteristics within the first year of anastrozole therapy¹ stratified by upfront and switch therapy and assessment of the relationship of arthralgia incidence and arthralgia characteristics to patients' compliance.

The absolute number and percentage of patients with at least one event of arthralgia within pre-defined intervals (0-3, 3-6, 6-9, 9-12 and 12+ months after the start of anastrozole treatment) will be calculated.

Characteristics of arthralgias within each time interval will be evaluated descriptively stratified by upfront and switch therapy:

- Maximum intensity, localization, relationship to study drug, diagnostics and arthralgia management presenting number and percentage of each category.
- Time between start of anastrozole therapy and first incidence of arthralgia will be analysed using the Kaplan-Meier method.

Maximum duration of arthralgias will be evaluated descriptively, presenting standard statistics.

Retrospective assessment of incidence of pre-existing arthralgias before start of anastrozole treatment, stratified by upfront and switch therapy.

The absolute and percentage number of patients with pre-existing arthralgias will be calculated stratified by upfront and switch therapy.

Descriptive assessment of arthralgia therapy and of costs of arthralgia therapy, stratified by upfront and switch therapy.

Evaluation will be performed descriptively with standard statistics and associated with cost modules of sick funds.

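### The arthralgia module as listed holds no onset date and no source of onset is named, so arthralgias without an AE-form date cannot be placed reliably on the treatment clock

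*Protocol*

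**What the plan says.** **What the analysis needs.** Section 11.2, counting from the first anastrozole intake: "Each occurrence of arthralgia will be assigned to the corresponding time interval according to 0-3, 3-6, 6-9, 9-12 and 12+ months after the start". Section 11.4.1 counts patients with at least one arthralgia in each of these intervals and adds: "Time between start of anastrozole therapy and first incidence of arthralgia will be analysed using the Kaplan-Meier method". The time origin is available, because section 8.1.1 lists "Start date of anastrozole therapy" as a registration item.

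**What the arthralgia forms list.** The baseline module (8.1.2) reads "Arthralgia onset during anastrozole therapy (no, yes, unknown – if yes : localisation, swelling, pain intensity; duration, relationship to study drug". The follow-up module (8.1.3) has the same entry, and the discontinuation questions there are built the same way, with seriousness and outcome added. Start and end are mentioned only for the medication given for arthralgia.

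**What the patient is asked.** At the start (8.2.1): "Did you experience any arthralgias since you started anastrozole treatment? (no, yes". At study months 3, 6 and 9 (8.2.2): "Did you experience any arthralgias during the past three months? (yes, no".

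**How the two clocks relate.** Section 6: "Patients will have taken anastrozole for at least three months and not more than six months before the start of the study".

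**What the AE form lists.** Section 8.3.1.2 asks for a start date and a stop date for every adverse event in the observational period. Section 8.1.2 sends arthralgia arising after the start of anastrozole to a form it calls the Arthralgia AE module. Section 8.1.3 sends adverse events in general to a separately named AE/SAE module.

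**The concern.** Interval incidence and time to first arthralgia are both counted from the first tablet, so each event needs an onset date on that clock. The form designed for arthralgia does not list one. A duration does not supply it: once pain has resolved, duration gives the onset only if the end date is known, and neither an end date nor an ongoing flag is listed.

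The patient items do not fill the gap. The start item runs from the first tablet, but a woman enrolled in month 5 who answers yes could have had her onset in 0-3 or in 3-6 months. The follow-up item looks back three months from a study visit, and study visits lie 3 to 6 months off the treatment clock by an amount that differs between women. It also does not separate new pain from continuing pain.

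At stake is the onset pattern of arthralgia in the upfront and switch groups, a stated secondary objective. The 0-3 month interval is the most exposed: everyone enters after at least three months of drug, so all of it, and part of 3-6, lies before enrolment and rests on recall. A date that was never collected cannot be restored at the analysis stage.

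**Working it through.** The protocol gives no figure for this point, so there is none to reproduce. The check has two parts.

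**1. Can an onset date be found?**

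- Arthralgia module at baseline and follow-up, and the discontinuation questions: no date listed.
- Start and follow-up questionnaires: yes or no, no date.
- AE form (8.3.1.2): start and stop dates. Arthralgia on therapy meets the AE definition in 8.3.1.1.
- Link between them: none stated. The discontinuation questions grade causality in five levels and the AE form in two, so they are not the same form. Section 11.4.2 expects some events to be found only on other eCRF pages, without the details that the AE form asks for.

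Arthralgias with an AE form can therefore be dated and the others cannot. The protocol does not let one estimate the split.

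**2. How far off are undated events?**

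Let e be months on anastrozole at enrolment, assumed uniform on 3 to 6, and d = e − 3.

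*Follow-up windows, onset uniform within the window.* Each three-month window covers 3 − d months of one treatment interval and d months of the next.
- Midpoint placement is wrong with probability min(d, 3 − d)/3, which averages 0.75/3 = 25%.
- Visit-date placement is wrong with probability (3 − d)/3, which averages 1.5/3 = 50%.

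*Baseline window, onset uniform within the window.* The share outside 0-3 months is (e − 3)/e. Averaged over e this is 1 − 3 × (1/3) × ln(6/3) = 1 − ln 2 = 31%.

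*All first-year onsets, by simulation.* Assume 35.6% with arthralgia by month 12. Section 1.1 gives that figure for joint disorders on anastrozole, over a longer follow-up. Two onset shapes were used: constant hazard, and front-loaded (Weibull, shape 0.6). With S(12) = 1 − 0.356 = 0.644, the constant-hazard share for 0-3 months is 1 − 0.644^(3/12) = 10.4%. The Weibull share is 1 − 0.644^((3/12)^0.6) = 17.4%.

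| | Constant hazard | Front-loaded |
|---|---|---|
| True onset in 0-3 / 3-6 / 6-9 / 9-12 months, % of women | 10.4 / 9.3 / 8.4 / 7.5 | 17.4 / 7.8 / 5.8 / 4.7 |
| Share of first-year onsets before enrolment | 43% | 61% |
| Wrong interval, placed at window midpoint | 28% | 21% |
| Wrong interval, placed at visit date | 64% | 73% |

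With uniform onsets, or exponential onsets with mean 3 or 6 months, over the whole observation period, the ranges are 19-27% (midpoint) and 57-79% (visit date).

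Entry timing matters. If every woman entered at exactly 3 months, the windows would coincide with the intervals and nothing would be misplaced. If an onset date is recorded, no event is misplaced for lack of one.

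**The case against.** The strongest reply is that an onset date is collected. Arthralgia on therapy is an adverse event, the AE form asks for its start date, the baseline page routes arthralgia to a form with AE in its name, and the program plan in section 7.2 schedules the AE/SAE module at every visit while listing no separate arthralgia module. Onsets before enrolment also seem to be meant. Footnote 2 to the flow chart in section 7.1 counts the 3 to 6 months of earlier therapy within a 12 or 15 month observation period, and section 11.4.2 keeps events with onset from the start of anastrozole.

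Much of this stands. A reader might infer that most arthralgias cannot be placed, that the 0-3 month interval will be empty and that the curve will run late. The documents do not support that. It would need both no AE-form date and a rule that dates events by the visit. No such rule is stated, and section 11.2 assigns by time since treatment start. Nor does any section make the patient's three-month item the source for interval incidence: section 11.3 ties the determination of arthralgia incidence to CRF documentation, and the Kaplan-Meier curve uses only the first event, so repeated yes answers would not add events to it.

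It can also be said that section 8 is a content list. The eCRF pages and Appendices E and F are not at hand, and duration might be captured as dates, as it is for medication. This is possible and limits the point to the forms as listed.

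Finally, choosing among sources can be left to the SAP. That is fair for the choice itself, but not for a date that no form collected. What the reply does not supply is a requirement that every arthralgia in the module also gets an AE form, or a statement that the AE start date feeds the intervals and the curve.

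**Conclusion.** The point holds in a limited form. The Arthralgia module as listed has no onset date, the protocol names no source of onset, and arthralgias documented only there or in the questionnaire cannot be placed reliably in the planned intervals or on the curve. Arthralgias that also have an AE form can be placed.

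For undated events only, about 21-28% would land in the wrong interval by window midpoint and 64-73% by visit date. These figures assume uniform entry over 3 to 6 months, 35.6% with arthralgia by month 12 and one of the two onset shapes. They are not error rates for all arthralgias, because the share without an AE-form date is unknown. The endpoint is secondary and its p-values are descriptive, so this is a correction worth making before data collection and not a threat to the primary analysis.

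**What to change.** - Add an onset date (at least month and year) and an end date or ongoing flag to the Arthralgia module at baseline and follow-up and to the discontinuation questions. Alternatively, require a linked AE form with its start date for every arthralgia recorded.
- State in section 11.2 that this date, relative to the first tablet, is the source for both the interval assignment and the Kaplan-Meier analysis, and how events known only from the patient are handled.
- Report the patients' three-month item only as period prevalence by study visit, not as interval incidence.

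The cost is two fields in an existing eCRF module and a short addition to section 11.2. Onsets before enrolment will still be recalled, so the 0-3 month figures keep that weakness and should be labelled as retrospective.

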11.3 Description of analysis sets

The following analysis data sets will be used in the statistical analysis:

Safety population:

This population will consist of all patients enrolled at Visit 1 into this NIS who have taken at least one anastrozole tablet (with a documented date of 1st intake of anastrozole; if unavailable, date of 1st prescription of anastrozole may be used).

Intention-to-Treat (ITT) population:

This population will consist of all documented patients from the safety population for whom – based on CRF documentation - a determination of their compliance and/or incidence of arthralgias within the first 3 months after study start is possible.

Other analysis sets may be defined. Details about the definition of these additional analysis sets will be given in the SAP.

The ITT analysis set will be used for the primary analysis of compliance and arthralgias. The safety population will be the basis for the safety analyses and an additional secondary analysis of arthralgias.

Demographic data and all other important baseline characteristics will be presented for both, the ITT and safety analysis sets. The results will be presented in a descriptive way.

11.4 Method of statistical analysis

In this section, only the important statistical aspects of the statistical analysis of the outcome variables and the adverse events are presented. Details regarding the analysis will be presented in the SAP.

11.4.1 Outcome variables

The objectives outlined in chapter 3 will be analysed as follows:

Primary objective:

Assessment of arthralgia scores and patients' compliance within the first year of anastrozole treatment¹, stratified by upfront and switch therapy as well as assessment of the relationship between compliance and arthralgia scores.

The absolute number and percentage of compliant patients will be calculated. Groups will be compared with Fisher's exact test

From the arthralgia scores an overall score will be calculated (sum of 14 single item scores divided by 14). Groups will be compared using t-test.

Relationship between compliance and arthralgia scores will be assessed using logistic regression analysis.

Of primary interest are the 3 months data (data obtained within the first three months of anastrozole therapy). Secondly, the other time points will be evaluated.

Secondary objectives:

Incidence of arthralgias and arthralgia characteristics within the first year of anastrozole therapy¹ stratified by upfront and switch therapy and assessment of the relationship of arthralgia incidence and arthralgia characteristics to patients' compliance.

The absolute number and percentage of patients with at least one event of arthralgia within pre-defined intervals (0-3, 3-6, 6-9, 9-12 and 12+ months after the start of anastrozole treatment) will be calculated.

Characteristics of arthralgias within each time interval will be evaluated descriptively stratified by upfront and switch therapy:

- Maximum intensity, localization, relationship to study drug, diagnostics and arthralgia management presenting number and percentage of each category.
- Time between start of anastrozole therapy and first incidence of arthralgia will be analysed using the Kaplan-Meier method.

Maximum duration of arthralgias will be evaluated descriptively, presenting standard statistics.

Retrospective assessment of incidence of pre-existing arthralgias before start of anastrozole treatment, stratified by upfront and switch therapy.

The absolute and percentage number of patients with pre-existing arthralgias will be calculated stratified by upfront and switch therapy.

Descriptive assessment of arthralgia therapy and of costs of arthralgia therapy, stratified by upfront and switch therapy.

Evaluation will be performed descriptively with standard statistics and associated with cost modules of sick funds.

The assessment of compliance and of arthralgia therapy will be compared to and validated by the corresponding data obtained by the sick funds of the patients.²

For the subgroup of patients who consented to the data transfer of her sick funds data related to compliance and arthralgia therapy will be analyzed for correlation to the transferred data and described descriptively with standard statistics.

Assessment of subjective perception of side-effects by the patients, stratified by upfront and switch therapy.

Scores of GASE-P and SASS will be evaluated by presenting number and percentage of each category stratified by upfront and switch therapy. Groups will be compared using chi-square test.

Identification of factors influencing and correlating to treatment-emergent arthralgias, such as patient's characteristics (e.g. age, BMI), disease characteristics, duration of anastrozole treatment, subjective perception of side-effects by the patients etc.

Patient characteristics, disease characteristics and duration of anastrozole treatment will be described descriptively stratified by the occurrence of treatment-emergent arthralgias. A possible influence will be analyzed using logistic regression.

Identification of factors influencing and correlating to patients' compliance; for example patient's characteristics (age), disease characteristics, concomitant medication, subjective perception of side-effects by the patients, incidence and characteristics of arthralgias (time between start of anastrozole therapy and occurrence, intensity and duration of arthralgias), incidence of AEs etc.

Evaluation will be performed in the same way as described for the previous criterion.

Compare time to progression (TTP) between patients with arthralgias and patients without arthralgias in the first year of anastrozole treatment, stratified by upfront and switch therapy.

Time between start of anastrozole therapy and progression of disease will be analysed using the Kaplan-Meier method comparing patients with arthralgias to patients without arthralgias and upfront therapy to switch therapy.

Assessment of safety and tolerability of anastrozole.

The safety analysis will be descriptive and comprise all documented adverse events.

The ITT analysis set will be used for the primary analysis of compliance and arthralgia scores. The safety population(s) will be the basis for the analysis of costs and safety analyses and for a secondary analysis of arthralgia scores. Additionally, all women who completed this NIS and who were compliant according to the criteria defined in the protocol for the total duration of 12 months of anastrozole treatment will be analysed separately with regard to the arthralgia characteristics (VAS score, incidence, intensity etc), side-effect management, related costs, perception of side effects etc.

¹ The start of the adjuvant treatment with anastrozole is defined by the date of the first tablet intake. If this date is not assessible, the date of the first prescription of anastrozole can be used instead.

² This is only applicable to patients who consented to data transfer and who are insured by sick funds who joined the respective contract. Data transferred from the sick funds will include breast-cancer related costs from 12 months before study start up to the end of the study for the respective patient.

